measures of treatment effect will include treatment retention, Addiction Severity Index (ASI)-Lite score, Hamilton Depression Rating Scale (HAM-D) score, Brief Substance Craving Scale (BSCS) score, Methamphetamine Withdrawal Questionnaire (MAWQ), Clinical Global Impression scores as assessed by the subject (CGI-S) and an observer (CGI-O) and HIV risk taking behaviors using an HIV Risk-Taking Behavior Scale (HRBS). ASI-Lite is performed during screening and at study termination. The HAM-D is performed biweekly through screening, baseline, and treatment periods; it is also performed at study termination. The BSCS, CGI-S, and CGI-O are assessed weekly at screening, baseline and during treatment and also at study termination. The MAWQ is collected 3 times per week during baseline and the first two weeks of treatment and then weekly thereafter. The HRBS is assessed at screening and at study termination. There will also be neurocognitive battery done at screening and at study termination. Study agent compliance will be monitored by reconciliation of dispensed study agents. Treatment effects on other substances of abuse (amphetamines, cocaine, opiates, tetrahydrocannabinol, barbiturates, and benzodiazepines) will be determined by quantitative urinalysis at a central laboratory.

ANALYSIS: Each of the primary and secondary outcome variables will be analyzed using appropriate statistical methods for the intent-to-treat population and for the evaluable population. The intent-to-treat population includes subjects who are randomized and receive at least 1 dose of study agents. The evaluable population is those subjects who meet eligibility criteria and provide at least 6 urine specimens and 28 days of self-report of substance use (SUR). The individual effects, if any, of age, race, usual route of methamphetamine use (oral/nasal inhalation *versus* intravenous/smoked), and clinical site on the primary treatment effects will be determined where numbers permit. Interactions of these variables with gender, historical self-report of methamphetamine use (prior use in the last 30 days ≤ 18 *versus* > 18), and severity of depression (HAM-D score ≤ 12 *versus* >12) will also be assessed. Statistical tests will be two-sided at a 5% Type I error rate. Confidence intervals will be two-sided with a 95% confidence coefficient.

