13.6.28 Cognitive Battery

This battery of tests is designed to evaluate memory, attention, perceptual speed, and aspects of executive function. Tests have been selected for ease of administration, length, and sensitivity to the deficits found with stimulant abusers (Simon et al, 1999). These assessments will be collected once during the screening/baseline period and at treatment discharge. Each participant will be tested twice on all of the tests with the exception of the Repeated Memory Test (RMT). RMTs are tests that show an effect of repeated administration (Basso, 1999). Two forms of the RMT will be administered.

The participants are shown the RMT memory cards, then given the Trails A & B, then the digit symbol. At this point 10 minutes have passed and they are given the recall, the recognition test and the Stroop. The D2 test of Attention takes an additional 8 minutes. The total time to administer the battery is about 25-30 minutes.

Trail Making A, B. The Trail Making tests tap attention, sequencing, psychomotor speed, and mental flexibility. Trail Making A requires the participant to connect 25 numbers, randomly arranged on a page, in proper order by drawing lines between them. Test B consists of 25 alternating letters and numbers. The participant connects the items (e.g. 1,A,2,B,3,C) by drawing lines. The dependent measure is time (Reitan, 1958; Giovagnoli, 1996).

WAIS-R Digit Symbol sub-test. Digit Symbol sub-test, (Wechsler, 1981) is a measure of psychomotor speed and manipulation of information. The participant is given 90 seconds to fill in the symbols that correspond to a page of numbers using a key with nine numbers and nine corresponding meaningless geometric symbols.

Stroop. Stroop measures selective attention and the ability to ignore irrelevant information by measuring the ease with which a person can conform to changing demands suppress a habitual response in favor of an unusual one (Golden, 1978; Stroop, 1935; MacLeod, 1991).

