15.4.2 Secondary Outcomes Measures

Effect on methamphetamine and other drug use during the 12-week treatment period

- **A.** Log weekly median quantitative methamphetamine level.
- **B.** The proportion of successful subjects with different patterns in the reduction in drug use examined as follows:
 - 1. Proportion of subjects with 3 consecutive weeks of abstinence as measured by 9 consecutive methamphetamine negative urine samples.
 - 2. Proportion of subjects who reduce the overall proportion of methamphetamine quantitative urine concentration to 50% or less of his/her baseline rate.
 - 3. Proportion of subjects who reduce the overall proportion of methamphetamine quantitative urine concentration to 25% or less of his/her baseline rate.
- **C.** Weekly mean proportion of methamphetamine non-use days based on subjects self report of use (SUR) during the 12-week treatment period.

- **D.** The maximum number of consecutive methamphetamine non-use days by subjects self report of use (SUR).
- **E.** The proportion of methamphetamine negative urines during the 12-week period.
- **F.** Weekly mean proportion of non-use days of other drug use, by other drug according to SUR.
- G. Proportion of negative urines or alcohol breathalyzer results for other drug use, by drug.

Reduction in the severity of methamphetamine dependence, craving, and withdrawal

- H. CGI-O scores.
- I. CGI-S scores.
- J. ASI-Lite scores.
- K. BSCS scores.
- L. MAWQ scores

Severity of Depression

M. HAM-D scores.

Changes in Cognitive Functions

N. Change in cognitive function at study end compared to baseline.

HIV Risk Taking Behaviors

O. Change in HRBS scores since baseline.

Treatment Retention

P. Number of days in treatment.

Safety of Bupropion

Q. AEs, laboratory data, physical exams, and vital signs.

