15.6 ANALYSIS PLAN

15.6.1 Efficacy Assessments

Each of the primary and secondary efficacy outcome measures will be analyzed for the intent-totreat and for the evaluable population. Major differences in the results, if any, will be further explored. While there is every intent to be complete in describing the analyses to be performed, it is not possible to anticipate every contingency and some adjustments may be required to meet constraints posed by the structure of the data.

Statistical tests will be two-sided at a 5% Type I error rate. Confidence intervals will be two-sided with a 95% confidence coefficient.

Primary Efficacy Outcomes

The weekly mean proportion of methamphetamine-free urines on study will be compared between treatment groups using Generalized Estimating Equations (GEE) for ordinal categorical response (Lipsitz *et al.*, 1994). GEE provide a model-based regression method applicable for the analysis of the correlated data that will result from this repeated measures longitudinal study. The GEE procedure was first proposed by Liang and Zeger (1986) and Zeger and Liang (1986) and models the population average. GEE has several useful features:

- 1. It can be used to analyze different types of outcomes such as continuous, binary, or count.
- 2. It can be used to analyze an unbalanced design caused by either differing numbers of observations per person or by observations taken at different times.
- 3. The parameter estimates are consistent even if assumptions about the variance structure are not completely accurate.

As a secondary analysis, the individual effects, if any, of age, race, site, and usual route of methamphetamine use (oral/nasal inhalation versus intravenous/smoked) on the primary treatment effects will be determined where numbers permit. The first order interactions of these variables with gender, historical self-report of methamphetamine use (prior use in the last 30 days ≤ 18 versus > 18), and severity of depression (HAM-D score ≤ 12 versus >12) will also be included in the model. Presentation will include the full model with all terms and a reduced model containing only significant terms.

Secondary Efficacy Outcomes

Unless the primary response analysis implies the need for a more elaborate model, between group comparisons of the secondary outcomes will be performed as follows:

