- 1. Log weekly median quantitative methamphetamine, weekly mean proportion of methamphetamine non-use days by self-report, weekly mean proportion of non-use day of other drug use, measures A, C, and F, will be assessed by GEE.
- 2. Proportion of successful subjects and negative urines for other drugs or alcohol breathalyzer tests, measures B and G, will be assessed by Chi-square tests.
- 3. The maximum number of consecutive methamphetamine non-use days, proportion of methamphetamine negative urines, change in cognitive function, and change in HRBS scores at termination compared to baseline measures D, E, N, and O will be assessed by t-test.
- 4. Repeated measures of CGI-S, CGI-O, BSCS, ASI-Lite, MAWQ, and HAM-D scores, measures H, I, J, K, L, and M will be assessed by GEE.
- 5. Survival analysis will be performed on retention data (measure P). The Wilcoxon (Gehan) test will be used to test the hypothesis that the survival distribution of the bupropion group will be the same as those of the placebo group.
- 6. Adverse events, laboratory data, physical exams, and vital signs will be reported in tabular form. AEs will be listed indicating the frequency of each type of event by various demographic characteristics such as gender, ethnicity, age, duration of addiction, other medical problems both related to and independent of the addiction, and combinations of these characteristics. The frequencies of adverse events by type will be compared between study arms using Chi-square analyses.

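### Change in cognition (N), change in HRBS (O) and the 12-week proportion of negative urines (E) are compared by t-test; ANCOVA on baselines already collected would be more precise

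*Protocol*

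**What the plan says.** The Protocol, 15.4.2, defines measure E as "The proportion of methamphetamine negative urines during the 12-week period", N as "Change in cognitive function at study end compared to baseline" and O as "Change in HRBS scores since baseline". Section 15.6.1, item 3, then fixes the method: "change in HRBS scores at termination compared to baseline measures D, E, N, and O will be assessed by t-test". Measure D shares that sentence but is not part of this point.

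The one qualifier attached to the list of secondary methods is "Unless the primary response analysis implies the need for a more elaborate model". Its trigger is the primary response analysis, not the needs of these outcomes. Section 16.3 adds that the final analysis will follow the analytical plan section of the Protocol.

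A baseline exists for each of the three measures:
- **Cognition (N):** section 13.6.28 says "These assessments will be collected once during the screening/baseline period and at treatment discharge".
- **HRBS (O):** assessed at screening and at termination (section 3; also 13.1 and 13.4).
- **Urine (E):** at least four specimens, ideally six, in a consecutive two-week period, at least one of them positive (13.2). After randomisation the stored baseline specimens go to the same central laboratory as the on-treatment specimens (13.6.14).

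**The concern.** A t-test on change fixes the slope on baseline at 1. Unless the baseline to follow-up relation is that steep, the subtraction adds baseline noise to the comparison. When r is below 0.5 (equal variances), a change score is noisier than ignoring the baseline altogether. The raw t-test for E goes the other way and leaves out two weeks of pre-treatment urine results.

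What is at stake is precision. Section 15.7 reports that the sample was raised from 100 to 150 to obtain more information after higher than expected dropout, and that the results are to guide the choice and design of further studies. Wider intervals than necessary on N, O and E work against that purpose, and the data that would narrow them are already in the database.

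**Working it through.** **Figures in the plan.** There is none to reproduce. Section 15.7 says the sample size could not be calculated statistically, and no effect size, SD or power is given for E, N or O.

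**Inputs**
- Two-sided 5% tests: 15.6.1.
- 150 randomised: section 3. A 1:1 split, 75 per arm, is assumed.
- Correlation r between baseline and follow-up: not in the Protocol. Assumed range 0.3 to 0.8.

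**Formulas.** Take equal variance s² at baseline and follow-up. The variance of the treatment contrast is then proportional to:
- raw follow-up: s²
- change score: 2s²(1−r)
- ANCOVA: s²(1−r²)

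So ANCOVA/change = (1−r²)/[2(1−r)] = (1+r)/2, and ANCOVA/raw = 1−r².

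**Results (s² = 1)**

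| r | Raw | Change | ANCOVA | ANCOVA/change | ANCOVA/raw |
|---|---|---|---|---|---|
| 0.3 | 1 | 1.40 | 0.91 | 0.65 (35% less) | 0.91 (9% less) |
| 0.5 | 1 | 1.00 | 0.75 | 0.75 (25% less) | 0.75 (25% less) |
| 0.7 | 1 | 0.60 | 0.51 | 0.85 (15% less) | 0.51 (49% less) |
| 0.8 | 1 | 0.40 | 0.36 | 0.90 (10% less) | 0.36 (64% less) |

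The two gains move in opposite directions. ANCOVA gains most over change scores when r is low, and most over raw values when r is high.

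**In subjects.** At r = 0.5 both ratios are 0.75, and 0.75 × 75 = 56.25, so 57 per arm with adjustment match 75 per arm without. Equivalently, 1/0.75 − 1 = 33% more subjects.

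**In power.** With 75 per arm, a raw t-test has 80% power for an effect of (1.960 + 0.842)/√(75/2) = 0.457 SD. For that same effect:

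| r | Change score | ANCOVA |
|---|---|---|
| 0.3 | 0.658 | 0.836 |
| 0.5 | 0.800 | 0.899 |
| 0.7 | 0.951 | 0.975 |

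**Simulation check.** With 39 per arm and 4000 replicates, r = 0.3 / 0.5 / 0.7 gave ANCOVA/change of 0.68 / 0.76 / 0.86 and ANCOVA/raw of 0.93 / 0.76 / 0.51. The formulas therefore hold closely in samples well below 75 per arm.

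**Measure E.** Eligibility requires at least one positive among four to six baseline specimens, so the baseline proportion of negatives is cut off below 1 and is measured coarsely. Both features lower r and place E towards the 9% end of the raw comparison.

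**The case against.** The strongest reply is that nothing here is invalid. Both t-tests are unbiased under randomisation, and N and O already use the baseline through the change score; only E ignores it. These are secondary measures in a study that section 15.3 presents as exploring response and section 15.7 as preliminary. Section 8.2 even says HRBS is not a secondary outcome, while 15.4.2 lists it as measure O; that conflict is a separate matter. The size of the gain rests on a correlation the Protocol does not supply. All of this stands, and it limits the point to efficiency.

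It does not remove the point. Item 3 names the t-test, so this is a stated method and not a detail left open for a statistical analysis plan. The qualifier on the secondary methods does not commit anyone to baseline adjustment.

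A reader might infer three stronger things, which the Protocol does not support:
- **That half the data for these outcomes are lost.** The 46%–50% in section 15.7 is dropout. Sections 12.6, 12.12.1 and 13.4 ask subjects who leave early to complete the termination assessments, which include HRBS and the cognitive tests. How many do so is not stated. E uses specimens from the whole 12 weeks and needs no termination visit.
- **That GEE is wrong for ASI-Lite.** Item 4 lists it under "Repeated measures of CGI-S, CGI-O, BSCS, ASI-Lite, MAWQ, and HAM-D scores", and the synopsis says "ASI-Lite is performed during screening and at study termination". Two observations per subject are repeated measures, and GEE can handle them.
- **That the GEEs for CGI-O, CGI-S, BSCS, MAWQ and HAM-D wrongly omit the baseline score.** Item 4 names the method and excludes no covariate. How the baseline enters is ordinary statistical analysis plan detail.

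**Conclusion.** The point holds for N, O and E as an avoidable loss of precision. Against change scores (N, O), ANCOVA lowers the variance by 35% at r = 0.3, falling to 10% at r = 0.8. Against the raw value (E), the reduction is 9% at r = 0.3 and 64% at r = 0.8, with E probably near the low end.

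The direction does not depend on r, apart from the few degrees of freedom spent. The size does, and r is an assumption throughout. The change-score ratio also assumes equal variances at baseline and follow-up. Adjustment does not solve missing termination assessments, and the primary analysis is untouched. It would be wrong to read this as a finding of bias: the planned tests estimate the treatment difference without bias, only less precisely than the collected data allow.

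**What to change.** Amend item 3 of the Secondary Efficacy Outcomes in 15.6.1:
- **N and O:** ANCOVA of the termination value on treatment, the baseline value of the same measure and the three randomisation factors in section 8.4 (gender, prior 30-day use stratum, HAM-D stratum).
- **E:** the same model for the 12-week proportion of negative urines, with the baseline proportion of negative urines as covariate. Take that proportion from the central laboratory results, with the same cut-off as for the on-treatment specimens, and not from the on-site device used for eligibility.

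The cost is a sentence or two of text and a few degrees of freedom. No new data, visits or assays are needed.

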3 PROTOCOL SYNOPSIS

STUDY OBJECTIVES: To assess the efficacy and safety of bupropion in reducing methamphetamine use in subjects with methamphetamine dependence. It is hypothesized that bupropion treatment, compared to placebo, will be associated with fewer days of methamphetamine use as measured by quantitative urine analysis for methamphetamine.

STUDY DESIGN: This is a double-blind, placebo-controlled, parallel-group design study in which, after screening and a 2-week baseline period, 150 subjects will be randomly assigned to either placebo or bupropion for 12 weeks with a follow-up assessment 4 weeks after treatment completion. Five clinical research sites will each recruit approximately 30 participants into the trial. Adaptive randomization will be used to balance treatment groups based on gender, historical self-report of methamphetamine use (prior use in the last 30 days \leq 18 *versus* > 18), and severity of depression (HAM-D score \leq 12 *versus* >12).

STUDY POPULATION: 150 individuals (30 per site) with Diagnostic and Statistical Manual of Mental Disorders Fourth Edition (DSM-IV) criteria for methamphetamine dependence determined by structured clinical interview (SCID) will be randomized into one of two treatment groups. Males and females, between 18 and 65 years-of-age, with 1 methamphetamine positive urine specimen provided during the 2-week baseline period prior to randomization who verbalize the ability to understand and provide written informed consent will be included.

TREATMENTS: Subjects randomized to bupropion treatment will receive 150 mg of sustainedrelease bupropion once daily for 3 days then twice daily for a total of 300 mg for a total of 12 weeks (dose taper will be performed the last 3 days of the 12 weeks to 150 mg per day). Subjects randomized to the placebo arm will receive matched placebo tablets according to the same schedule. All subjects will receive manual-guided cognitive behavioral therapy (CBT) thrice weekly during the 12 weeks of treatment.

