13.6.18 Adverse Events (AEs)

AEs will be assessed and recorded at each visit by an investigative staff nurse or physician or qualified research assistant. If an AE that requires medical attention is reported to a nurse or research assistant, it will be reported to a study physician immediately. A study physician will meet with the subject once a week to review the AEs recorded by the nurse and to assess for any additional AEs. The investigator or study physician will assess subjects for any medical or psychiatric side effects. Both the staff nurse, research assistant or the physician will assess AEs by asking the participant "How have you been feeling since I saw you last". The type of AE, severity of the AE, and the relationship to the study treatments will be recorded on an AE CRF according to the procedures described in section 13.6.

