14.6 ADVERSE EVENTS REPORTING

In accordance with FDA reporting requirements, all AEs occurring during the course of the clinical trial will be collected, documented, and reported by the principal investigator or sub-investigators according to the specific instructions detailed in this section of the protocol and Appendix III. The occurrence of AEs will be assessed at each study visit and an AE CRF completed weekly.

An AE is defined as any reaction, side effect, or untoward event that occurs during the course of the clinical trial, whether or not the event is considered medication-related or clinically significant. For this study, AEs will include events reported by the subject, as well as clinically significant abnormal findings on physical examination or laboratory evaluation. A new illness, symptom, sign or clinically significant clinical laboratory abnormality or worsening of a pre-existing condition or abnormality is considered an AE. Stable chronic conditions, such as arthritis, which are present prior to clinical trial entry and do not worsen are not considered AEs. All AEs must be recorded on the AE Form. The AE Form is also used to record follow-up information for unresolved events reported on previous visits.

Each week, a study investigator must review the AE Form completed for the previous week for any events that were reported as continuing. All AEs, including clinically significant abnormal findings on laboratory evaluations, regardless of severity, will be followed by study investigators until satisfactory resolution. AEs should be reported up to 4 weeks following completion of, or termination from treatment.

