15.7 SAMPLE SIZE CALCULATION

The study sample size was planned to be 50 subjects in each treatment arm. As the primary outcome measure had only begun to be used for methamphetamine dependence studies, it is not possible to statistically calculate sample sizes. The number of 50 subjects in each arm was selected based on other NIDA studies of substance abuse as a number that is sufficient to provide some indication of treatment effect during preliminary investigations. To substantiate the study

sample size selected, the data of the first fifty randomized subjects was to be used to obtain estimates of the treatment effect and its variance and to estimate the total number of subjects required for the study to have 80% power at the 5% significance level. Upon this analysis, NIDA would decide to take one of three possible actions: 1) Stop the trial, 2) Complete the study of 100 patients as per the original protocol, or 3) Increase the sample size to that estimated as needed to have a definitive result.

Upon preparation of the blinded analysis of the first fifty randomized subjects for DSMB review in April 2004, it was determined that the dropout rate was 46%-50%, which was higher than expected. Thus, NIDA proposed to extend the study to 150 patients instead of 100 patients to be able to increase the amount of patient information available with approximately 12 weeks of data; this will make NIDA's evaluation more certain as to whether or not to further study the Bupropion/methamphetamine combination therapy, and, if further studied, assist in the choice of a future study design and power requirements.

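### The adverse-event chi-square takes no account of observed time, so it is distorted if early departure, already at 46%-50% overall, differs between arms

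*Protocol*

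**What the plan says.** Safety is the first secondary objective (Protocol 5.2 and 15.2). The only between-arm safety test named is in item 6 of the secondary analyses in 15.6.1: "The frequencies of adverse events by type will be compared between study arms using Chi-square analyses". The general rule in the same section applies to it: "Statistical tests will be two-sided at a 5% Type I error rate". Section 16.3 states that the analysis follows the protocol's own analytical plan.

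On collection, section 13.6.18 says that "AEs will be assessed and recorded at each visit by an investigative staff nurse or physician or qualified research assistant", with visits three times a week, and section 14.6 says that "The occurrence of AEs will be assessed at each study visit and an AE CRF completed weekly". Collection continues after exit, also under 14.6: "AEs should be reported up to 4 weeks following completion of, or termination from treatment". Sections 12.5, 12.6 and 12.12.1 ask early leavers for termination assessments. Sections 12.7 and 12.12.1 add a contact 4 weeks after discharge, by telephone if needed.

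On retention, the synopsis states that "150 subjects will be randomly assigned to either placebo or bupropion for 12 weeks". Section 15.7 reports of the first fifty randomised subjects that "it was determined that the dropout rate was 46%-50%, which was higher than expected". Retention is secondary measure P in 15.4.2 ("Number of days in treatment") and is tested by survival methods in item 5 of 15.6.1. That result is not linked to the adverse-event comparison.

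**The concern.** The number of subjects in whom an event is found depends on the event rate and on how long each subject is watched. A chi-square on frequencies uses only the first. A subject who leaves in week 3 is covered for about 3 + 4 = 7 weeks and a completer for about 12 + 4 = 16.

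If one arm keeps its subjects longer, it accumulates more first events at the same hazard and looks less safe. In the other direction, a real excess is diluted if the arm that carries it also loses more subjects. The plan already handles unequal follow-up elsewhere: 15.6.1 justifies GEE partly by unequal numbers of observations per person, and analyses retention as survival data. The stated safety comparison has no such allowance.

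**Working it through.** The protocol gives no adverse-event rate, no dropout figure by arm and no sample-size calculation, so there is no stated result to reproduce. Its one relevant figure is observed: 46%-50% of 50 is 23 to 25 subjects.

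**Inputs from the protocol.** Treatment lasts 12 weeks (synopsis), collection continues 4 weeks after exit (14.6), and pooled blinded dropout is 46%-50% (15.7).

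**Assumptions.** Dropout is 40% v 56%, whose midpoint is 48%. Dropout is exponential over 12 weeks and independent of adverse events. The event hazard h is constant, equal in both arms, unchanged after exit, and 0.02, 0.05 or 0.10 per week. The post-exit window f is 0 weeks (treatment visits only) or 4 weeks (every leaver reached).

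**Step 1, observed time.** With λ = −ln(1−d)/12, mean time on treatment is d/λ.

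- d = 0.46: 0.46/0.0513 = 8.96 weeks; d = 0.50: 0.50/0.0578 = 8.66 weeks. Adding 4 gives 12.96 and 12.66 of 16.
- d = 0.40: 0.40/0.0426 = 9.40 weeks; d = 0.56: 0.56/0.0684 = 8.19 weeks. The ratio is 1.15 on treatment and 13.40/12.19 = 1.10 with the window.

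**Step 2, crude proportion with at least one event.**

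Risk = 1 − e^(−hf) × { λ/(λ+h) × [1 − e^(−12(λ+h))] + e^(−12(λ+h)) }

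| h per week | f (weeks) | 40% dropout | 56% dropout | Risk ratio |
|---|---|---|---|---|
| 0.02 | 0 | 16.9% | 14.8% | 1.14 |
| 0.05 | 0 | 36.2% | 32.0% | 1.13 |
| 0.10 | 0 | 57.5% | 51.5% | 1.12 |
| 0.02 | 4 | 23.3% | 21.3% | 1.09 |
| 0.05 | 4 | 47.8% | 44.4% | 1.08 |
| 0.10 | 4 | 71.5% | 67.5% | 1.06 |

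The true hazard ratio is 1.00 in every row. With 48% dropout in both arms, the risk ratio is 1.00 in all six cases.

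**Step 3, sensitivity to the gap.** This takes 75 subjects per arm (assumed), 12-week event risks of 10%-50% and a two-sided 5% test.

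- 43% v 53%: risk ratio 1.05-1.06 with the window and 1.08-1.09 without; rejection 5.2%-6.5% over both.
- 38% v 58%: risk ratio 1.09-1.12 with the window and 1.16-1.19 without; rejection 5.7%-8.6% and 6.0%-11.2%.

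**Step 4, masking.** Take a true rate ratio of 1.5 in the arm with 58% dropout against 38%, and 12-week risks of 20%-40%. The crude risk ratio is 1.20-1.27 with the window (1.32-1.41 at equal dropout), and 1.16-1.21 without (1.36-1.43 at equal dropout).

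**Step 5, early events.** If the hazard runs only in weeks 0-2 (30% risk) and dropout is 38% v 58%, the proportions are 28.9% v 28.1% without the window and 30.0% v 30.0% with it.

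**Step 6, choice of denominator.** Suppose first events are divided by all observed treatment time. Step 2 then gives 1.141/1.148 = 0.99 at h = 0.02 and 1.116/1.148 = 0.97 at h = 0.10, not 1.00. For the early events of step 5, the crude ratio of 1.03 over a time ratio of 9.54/8.02 = 1.19 gives about 0.87, a spurious difference. If each subject's time stops at the first event, expected time at risk is Risk/h in each arm. The rate is then h in both arms and the ratio is exactly 1.00 in the constant-hazard cases.

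**The case against.** The strongest reply is that the crude proportion is a legitimate summary for a fixed-length trial that describes itself as preliminary. Retention by arm, missing observations by arm and a retention test are already planned, so a reader could judge unequal exposure. Section 15.6.1 allows adjustments, and exposure-adjusted rates are often left to an analysis plan, which is not at hand. This stands as a reason to keep the chi-square. It does not remove the point, because the protocol fixes that test as its only between-arm safety comparison and 16.3 directs the analysis to it. A separate retention test does not correct the event comparison.

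Four stronger readings are tempting, but the protocol does not support them.

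- A reader might infer that events are seen only while subjects attend. Sections 12.7, 12.12.1 and 14.6 extend collection to 4 weeks after exit, and 12.6 keeps subjects who stop the agent but stay in therapy on their scheduled assessments.
- A reader might infer that the comparison is biased as it stands. The dropout figure is pooled and blinded, so a difference between arms is only a possibility.
- A reader might infer that treatment is expected to change retention. Retention is measured and tested, but the hypotheses in 15.3 do not mention it.
- A reader might infer that an event lasting several weeks is counted once per weekly form. Section 14.6 uses the form to follow up unresolved events, and nothing says that such entries are counted again. The text does leave open whether the frequencies count subjects or events.

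**Conclusion.** The point holds in a conditional and modest form. The planned chi-square ignores observed time in a trial where about half of the first fifty subjects left early. If dropout were 40% v 56% with equal constant hazards of 0.02-0.10 per week, the better-retained arm would show a crude risk ratio of about 1.06-1.09 if all leavers are reached at 4 weeks, and 1.12-1.14 if none are. Partial success in reaching them would fall between. The distortion is nil at equal dropout, almost nil for events confined to the first weeks, and larger with a wider gap. The figures rest on an assumed split by arm, constant hazards that persist after exit, and dropout independent of adverse events. If adverse events themselves cause dropout, the relation is more complex and these figures do not describe it. Whether retention differs by arm will not be known before unblinding, so the allowance should be specified in advance.

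**What to change.** Amend item 6 of 15.6.1 as follows.

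- Keep the chi-square, and state that it compares the proportion of subjects with at least one event of each type, each subject counted once.
- Add beside it first events per subject-week at risk from first dose. Each subject's time ends at the first event of that type or at the last adverse-event contact, whichever comes first. Report a rate ratio with 95% CI, or equivalently a hazard ratio for time to first event with censoring at the last contact. Do not divide first events by all observed time (step 6).
- Tabulate observed weeks by arm.

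The cost is a change of wording and a few extra table columns. Visits and adverse events are already recorded, and no visit changes. The downside is small: the added comparison assumes that dropout is independent of adverse events, and the rate version also assumes a roughly constant hazard. That is why the crude proportion stays beside it.
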